1 STUDY SYNOPSIS

STUDY DESIGN

This is a two phased study that will include Phase A (complete) and Phase B.

Phase A

The primary objective of Phase A was to develop a patient-reported outcome (PRO) instrument that assessed erythropsia after LDD light treatments, the "Daily Life Erythropsia Questionnaire" (DLEQ). This was a non-interventional, cross-sectional study at 1-3 sites with primary data collection from patients who had undergone cataract surgery with implantation of the RxSight LAL and had treatment performed with the Light Delivery Device. Phase A was designed to use approximately English speaking patients at sites in the European Union where the device has a CE Mark.

Qualitative research interviews were conducted with adult patients who reported experiencing erythropsia to their eye care provider after treatment with the Light Delivery Device. These patients were identified, invited to participate, and interviewed within 8 weeks of a report of the erythropsia symptom. Cognitive debriefing methods were used during the interviews: (1) to ensure the questionnaire captures relevant aspects of erythropsia from the patient perspective, (2) to evaluate the clarity of each question, and (3) to assess response options for each question to ensure options capture the range of patient experiences (e.g., frequency, light conditions). Cognitive interviews and qualitative coding were to be conducted in up to three rounds of interviews and analysis with about eight patients per round. This allowed an iterative approach to the cognitive interviews and instrument modification: the DLEQ was tested with patients in the first round of interviews; following participant feedback modifications were made to the DLEO; the revision was tested in the second round of patient interviews; based on participant feedback adjustments were made to the instrument. An optional third and final round of interviews was determined not to be needed as further changes were not required. The instrument was revised to incorporate patients' words to support its content validity and to increase the clarity and understandability of items that will be used to assess patient experiences with erythropsia.

There were no assessments of treatment effectiveness or safety associated with this phase for PRO development. There were no laboratory assessments associated with this research. This protocol was submitted to an Institutional Review Board(s)/Ethics Committee as required for studies with primary data collection from patients.

Patients treated in a commercial setting were evaluated using the following inclusion/exclusion criteria.

INCLUSION CRITERIA

- Adult patients (40 to 80 years of age) that had implantation of the RxSight Light Adjustable Lens (LAL™).
- Patient reported experiencing erythropsia to their eye care provider after treatment with the Light Delivery Device within the past eight weeks.
- Patient is able to read, write, speak, and understand English.
- Patient is willing and able to comprehend and sign a written informed consent prior to study entry.

EXCLUSION CRITERIA

- Patient has a clinically-relevant medical or psychiatric condition which, in the opinion
 of the investigator and/or coordinator, would interfere with completing the study
 including, but not limited to, sensory problems, cognitive impairment, acute mental
 illness or inadequately treated depression or anxiety.
- Complications during cataract surgery that would complicate evaluation of the erythropsia symptom.

[figure not shown]
Phase B

Phase B is a prospective, randomized, controlled, multicenter, post approval study of the RxSight LAL and LDD to be conducted at up to 15 clinical sites. It will begin after development of the "Daily Life Erythropsia Questionnaire" PRO is complete and has been accepted by FDA. This is a new enrollment study that is expected to last up to 30 months and include up to 12 study visits. Subjects will be randomized in a 2:1 ratio to receive either the RxSight LAL or a monofocal IOL (Control).

Patients who require cataract extraction and intraocular lens implantation will be screened for eligibility. If it is determined that the patient may be eligible to participate, study staff will explain the study purpose, procedures, risks/benefits and subject responsibilities to the potential participant. Written informed consent will be obtained prior to any study specific testing. The patient is enrolled upon signing the informed consent.

Subjects with preoperative corneal astigmatism of ≥0.75 D, without pre-existing macular disease, and meeting all inclusion/exclusion criteria will be randomly assigned in a 2:1 ratio to receive either the RxSight LAL or a commercially available monofocal IOL (Control).

Commencing at the Postop Week 3 visit, eyes will be refracted and undergo visual testing. Eyes implanted with the RxSight LAL will receive a power adjustment based on the manifest refraction. Eyes measured with a manifest cylinder of ≥ 0.50 D will receive a spherocylindrical treatment while eyes with <0.50 D of manifest cylinder will receive only a spherical treatment. Subjects implanted with the RxSight LAL will return 3 to 7 days after their first adjustment and the same measurements performed again.

adjustments and up to two lock-in treatments. All light treatments are separated by 3 to 7 days.

Postoperatively, all subjects will undergo complete ophthalmic examinations at regular intervals over a 6-month period. Masked examiners will be utilized at postop week 3 and postop month 6 to perform visual acuity and manifest refraction measurements. If a study eye is diagnosed with UV retinal damage, an additional follow-up exam will be added at 12 months postoperatively to confirm resolution or document sequelae, if any.

Subjects should be screened for eligibility and only eyes meeting all inclusion and none of the exclusion criteria will qualify for implantation. Only one eye per subject may be included in the study. At any time, the fellow eye may be implanted with any commercially available IOL including the RxSight LAL.

INCLUSION CRITERIA

- Must sign a written Informed Consent form and be willing to undergo cataract
 surgery for the implantation of an IOL with random assignment to either the RxSight-LAL or the monofocal control IOL.
- Between the ages of 40 and 80 inclusive on the day the cataract surgery is performed.
- Preoperative corneal cylinder ≥0.75 diopters (D) to ≤2.00 D or >2.00 D and ≤ 2.5 D of corneal cylinder with a steep axis between 70 degrees and 110 degrees.
- Study eye has best corrected distance visual acuity projected (by clinical estimate based upon past ocular history and retinal exam) to be 20/20 or better after cataract removal and IOL implantation.
- Study eye has clear intraocular media other than cataract.
- Willing and able to comply with the requirements for study specific procedures and visits.
- Study eye has average dilated pupil diameter of ≥7.0 mm.
- Able to complete a written questionnaire in English.
- Study eye requires an IOL power within the range available for the RxSight LAL.

EXCLUSION CRITERIA

- Study eye with pre-existing macular disease.
- Study eye with a history of uveitis.
- Study eye with corneal pathology or corneal dystrophy that is either progressive or sufficient to reduce BCDVA to worse than 20/20.
- Subjects with serious co-morbid conditions that in the judgment of the investigator
 makes inclusion in the study not in the best interest of the subject.

Other Key Safety parameters

- Rates of erythropsia at each visit beginning at Postop Week 3, as evaluated by the inoffice erythropsia assessment, in RxSight LAL eyes
- Rates of erythropsia at each visit beginning at Postop Week 3, as evaluated by the Daily Life Erythropsia Questionnaire (DLEQ), in RxSight LAL eyes
- Rates of tritan anomaly on the City University Color Test at each visit beginning at Postop Week 3, in RxSight LAL eyes
- Rates of all types of adverse events, including loss of best corrected distance visual acuity (BCDVA) of ≥2 lines from Postop Week 3 visit, in RxSight LAL eyes
- In specular microscopy sub-study compared between the RxSight LAL and Control group:
 - Rate of within-eye loss of ≥25% ECD from preoperative visit at Postop Week 3 and Postop Month 6
 - Rate of within-eye loss of ≥30% ECD from preoperative visit at Postop Week 3 and Postop Month 6
- Rates of findings on testing consistent with ultraviolet retinal damage per an independent expert
- Rates of findings on testing consistent with ultraviolet retinal damage per an independent expert

Subjects who agree to participate in the study will return for the listed follow-up examinations for the study eye:

Examination Schedule:

Evaluation	RxSight LAL	Control
Preoperative	Day -60 to Day -1	Day -60 to Day -1
Operative	Day 0, day of surgery	Day 0, day of surgery
Postop Day 1	Days 1 to 2 postop	Days 1 to 2 postop
Postop Week 1	Days 7 to 14 postop	Days 7 to 14 postop
Postop Week 3	Days 17 to 24 postop: Adjustment #1	Days 17 to 24 postop
Adjustment #2, if needed	3 to 7 days post Adjustment #1	
Adjustment #3, if needed	3 to 7 days post Adjustment #2	es and CHA the same of the same
Lock-in #1	3 to 7 days post final adjustment	

¹ Chen KC, Jung JJ, Aizman A. Solar Retinopathy: Etiology, Diagnosis, and Treatment. Retinal Physician, Volume 10, Issue: October 2013, pages 46-50.

Lock-in #2, if needed	3 to 7 days post lock- in #1	
Postop Months 1-2	7 to 14 days post final lock-in visit	Days 30 to 60 postop
Postop Month 6	Days 120 to 180 postop	Days 120 to 180 postop
Postop Month 12, if needed	Days 330 to 420 postop	

Clinical Parameters:

Clinical assessments when indicated will be performed in the following order:

- 1. Demographics
- 2. Daily Life Erythropsia Questionnaire (DLEQ) (RxSight LAL only)
- 3. Ocular history
- 4. History of Medications
- 5. Corneal Keratometry
- 6. Specular Microscopy (substudy)
- 7. Uncorrected distance visual acuity (UCDVA)
- 8. Manifest Refraction
- 9. Best corrected distance visual acuity (BCDVA)
- 13. Intraocular pressure
- 14. Slit Lamp Examination
- 15. Fundus Exam
- 16. Fundus Photos
- 18. Dilated pupil diameter
- 20. Adverse Events

ABBREVIATIONS AND DEFINITION OF TERMS

AE	Adverse Event
ANSI	American National Standards Institute
BCDVA	Best Corrected Distance Visual Acuity
CFR	Code of Federal Regulations
CI	Confidence Interval
CRF	Case Report Form
D	Diopter
DLEQ	Daily Life Erythropsia Questionnaire
ECC	Endothelial Cell Count
ECD	Endothelial Cell Density
ETDRS	Early Treatment Diabetic Retinopathy Study
FDA	Food and Drug Administration
GCP	Good Clinical Practice
ICH	International Conference on Harmonization
IDE	Investigational Device Exemption
IOL	Intraocular Lens
IOP	Intraocular Pressure
IRB	Institutional Review Board
LAL	Light Adjustable Lens
LDD	Light Delivery Device
M	Month
MR	Manifest Refraction
MRCYL	Manifest Refraction Cylinder
MRSE	Manifest Refraction Spherical Equivalent
OCT	Optical Coherence Tomography
OD	Right eye
OS	Left eye
PAS	Post-Approval Study
PCO	Posterior Capsular Opacity
PI	Principal Investigator
SAE	Serious Adverse Event
SD	Standard Deviation
SE	Spherical Equivalent
UADE	Unanticipated Adverse Device Effect
UCDVA	Uncorrected Distance Visual Acuity

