5.2 SAFETY PARAMETERS

The primary safety endpoints are:

- Median rate of endothelial cell density loss at postop month 6 compared to preoperatively compared between the LAL and Control group
- Percent of LAL eyes with UV retinal damage at postop month 6

Other Key Safety parameters

- Rates of erythropsia at each visit beginning at Postop Week 3, as evaluated by the inoffice erythropsia assessment, in RxSight LAL eyes
- Rates of erythropsia at each visit beginning at Postop Week 3, as evaluated by the Daily Life Erythropsia Questionnaire (DLEQ), in RxSight LAL eyes
- Rates of tritan anomaly on the City University Color Test at each visit beginning at Postop Week 3, in RxSight LAL eyes
- Rates of all types of adverse events, including loss of best corrected distance visual acuity (BCDVA) of ≥2 lines from Postop Week 3 visit, in RxSight LAL eyes
- In specular microscopy sub-study compared between the RxSight LAL and Control group:
 - Rate of within-eye loss of ≥25% ECD from preoperative visit at Postop Week 3 and Postop Month 6
 - Rate of within-eye loss of ≥30% ECD from preoperative visit at Postop Week 3 and Postop Month 6

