6.4.2.1 Postponement of Light Treatment Procedure(s)

LDD treatment should be delayed if any of the following new symptoms or changes in performance are noted;

- Color Vision Testing: Treatment should be delayed if the subject scores worse on Part 2 of the City University Color Test than the Pre-adjustment test for Tritan evaluation.
- Erythropsia Evaluation: With any score of 2 (red), the treatment should be delayed.
- Best Corrected Distance Visual Acuity: With any loss of BCDVA (unless the cause is known to be non-retinal) of 10 letters or more on an ETDRS (logMAR) chart compared to the Postop Week 3 BCDVA, treatment should be delayed.

- 6.4.2.2 Requirements for Additional Testing

Additional testing should be performed as soon as possible to evaluate whether UV-related retinal damage has occurred if any of the following is observed. will be performed in eyes that meet any of the following criteria:

- Significant erythropsia during in office erythropsia assessment (score of 2 (red))
- Significant erythropsia as indicated on responses to the Daily Life Erythropsia Ouestionnaire including:
 - o "severe" or "very severe" erythropsia on question 3, OR
 - o a response of "very bothersome" erythropsia on question 6, OR
 - o a response of "more than 7 days" on question 2
- Significant crythropsia as interpreted by the investigator based on spontaneous reports by the subject
- If the subject reports any level of erythropsia at the Postop Month 1-2 visit OR at any interim visit after the Postop Month 1-2 visit and <90 days after surgery based on results of the in office erythropsia assessment, the Daily Life Erythropsia Questionnaire or spontaneous verbal reports by the subject, the subject will be mailed a paper version of the Daily Life Erythropsia Questionnaire to self administer and return to the investigational site between 90-120 days after surgery. If responses to the Daily Life

² Azar D, Stark W, Dodick J, et al. Prospective, randomized vector analysis of astigmatism after three-, one-, and no-suture phacoemulsification. J Cataract Refract Surg 1997; 23:1164-1173.

Erythropsia Questionnaire indicate that there is erythropsia on question 1, the subject should have an unscheduled visit and testing should be performed.

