- Any level of erythropsia at any unscheduled visit at 3-months or later or at the Postop Month 6 based on results of the in office erythropsia assessment, the Daily Life Erythropsia Questionnaire or spontaneous verbal reports by the subject
- Has a tritan anomaly (tritan score >1 on Part II of the 3rd Edition City University Color Vision Test (CUT) when tritan score was 0 pre-treatment) or an increase in tritan score of >1 at any time after light treatment
- Has an unexplained loss of best corrected distance visual acuity ≥2 lines compared to prelight-treatment at any visit (scheduled or unscheduled) after the first light treatment

[figure not shown]

testing should be repeated at subsequent study visit(s) following the diagnosis of retinal phototoxicity to assess subsequent changes. If a study eye is diagnosed with UV retinal damage, an additional follow-up exam will be added at 12 months postoperatively. Diagnostic imaging/testing of the fellow eye may be performed if in the opinion of the investigator additional information will aid in evaluation or diagnosis.

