7.6.3 Additional Safety Analyses

The following safety outcomes will be summarized descriptively based on the observed data and actual lens implanted. Results will be presented for all the RxSight LAL eyes and the Control group eyes. The 95% confidence intervals for means or percentage may be presented, as appropriate.

Adverse Events

Number and percent of study eyes will be summarized for each reported ocular AE at the operative visit and each postoperative visit for the LAL group and Control group separately. Serious ocular AEs and the non-ocular serious AEs will be summarized in the same manner. Additionally, for each of the device related AE reported during the study, the number and

percent of study eyes reported with the event will be presented. The ocular adverse events will be listed for eyes, if applicable, with IOL implantation attempted but without implantation. Ocular adverse events will be reported separately for the fellow eye.

BCDVA

BCDVA will be presented with the number and percent of eyes who fall into each category of BCDVA at each visit (e.g. 20/20 or better, 20/25 or better, 20/32 or better, etc.). The mean and standard deviation (SD) of BCDVA letter score will also be calculated for each visit. Change in BCDVA from Postop Week 3 or from Preoperative will be presented at each visit as categorical outcomes of "Increase in 15 letters or more", "Increase in 10-14 letters", "Increase in 5-9 letters", "No change", "Decrease in 5-9 letters", "Decrease in 10-14 letters", and "Decrease in 15 letters or more The mean and SD of the change from Postop Week 3 or Preoperative will also be presented. Similarly, the mean change from the prior visit to the next visit will also be summarized in the same manner.

In-Office Erythropsia Assessment (RxSight LAL only)

The number and percent of eyes in each outcome of erythropsia assessment (0- white, 1-pink, or 2- red) will be presented. In addition, the number and percent of eyes with increases in the level of erythropsia from the Postop Week 3 visit will be presented.

Daily Life Erythropsia Questionnaire (RxSight LAL only)

Results of the Daily Life Erythropsia Questionnaire will be summarized descriptively at each visit the questionnaire is completed.

City University Color Test (RxSight LAL only)

[figure not shown]
Results of the City University Color Test will be reported as the number and percent of eyes that have tritan findings >1 on Part Two of the test.

Slit Lamp Examinations

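### The fellow eye may receive LDD light at any time, but the per-visit DLEQ erythropsia rate for LAL study eyes is not separated by that exposure

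*Combined protocol and SAP*

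**What the plan says.** The synopsis (Section 1, Phase B) restricts enrolment: "Only one eye per subject may be included in the study". It then leaves the other eye open: "At any time, the fellow eye may be implanted with any commercially available IOL including the RxSight LAL". The readable text sets no interval between the two eyes.

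Among the key safety parameters, Section 5.2 lists "Rates of erythropsia at each visit beginning at Postop Week 3, as evaluated by the Daily Life Erythropsia Questionnaire (DLEQ), in RxSight LAL eyes". The analysis in Section 7.6.3 is one sentence: "Results of the Daily Life Erythropsia Questionnaire will be summarized descriptively at each visit the questionnaire is completed". Section 6.7 gives the DLEQ to the LAL arm only. Subjects who still report erythropsia around the Month 1-2 visit are covered by Section 6.4.2.2, under which "the subject will be mailed a paper version of the Daily Life Erythropsia Questionnaire to self administer", for return between days 90 and 120.

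Section 6.4.2.2 also uses DLEQ answers and spontaneous reports as triggers for additional testing. The late trigger is "Any level of erythropsia at any unscheduled visit at 3-months or later or at the Postop Month 6", whether found in the office, on the DLEQ or by verbal report. The DLEQ and spontaneous-report triggers do not say which eye is meant. Testing of the fellow eye is left to the investigator's discretion.

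One provision does distinguish the eyes. For adverse events, Section 7.6.3 says: "Ocular adverse events will be reported separately for the fellow eye".

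**The concern.** The DLEQ is answered by a person about daily life, but its rate is reported by eye. A LAL-arm subject who has a second LAL during follow-up goes through an LDD course in the fellow eye while still completing DLEQs for the study. If that subject reports a tint arising from the fellow eye, nothing readable in Section 7.6.3 keeps it out of the study-eye rate.

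Two things are at stake. The first is the meaning of a key safety rate in a post-approval study whose second question concerns retinal damage from LDD treatment (Section 3). Control subjects do not complete the DLEQ, so no concurrent rate would reveal the effect. The second is which study eyes are sent for additional testing, and so how cases are found for the retinal-damage endpoint.

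**Working it through.** The plan states no expected DLEQ rate, and the sample-size inputs of Sections 7.1.1 and 7.1.2 are not in the readable text. There is therefore no figure to reproduce. The check has three parts.

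**1. Can fellow-eye light overlap the DLEQ visits?** Assume the fellow eye follows the protocol's own schedule (Section 6.4.2): first adjustment 17 to 24 days after surgery, one to three adjustments and one or two lock-ins, each 3 to 7 days apart. Let fellow-eye surgery fall on study day X.

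- First light: X+17 to X+24.
- Last light, shortest course (one adjustment, one lock-in): X + 17 + 3 = X+20.
- Last light, longest course (five treatments, four gaps): X + 24 + 4×7 = X+52.
- The Month 6 window is days 120 to 180 (Section 6.6). First light can fall by day 180 if X ≤ 180 − 17 = 163, and by day 120 if X ≤ 120 − 17 = 103.

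Overlap with scheduled DLEQ visits, and with the mailed DLEQ at days 90 to 120, is therefore possible.

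**2. Which erythropsia outcomes are tied to an eye?**

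- DLEQ rate: labelled by LAL eye in Section 5.2, with no reference to the fellow eye in Section 7.6.3.
- Spontaneous reports: triggers in Section 6.4.2.2, not one of the listed rates. The listed erythropsia rates are the in-office assessment and the DLEQ.
- Ocular adverse events: fellow eye reported separately.
- Exposure data: Table 1 takes ocular history preoperatively only, and no readable item names fellow-eye lens type or LDD dates. The CRFs themselves are not in the documents.

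**3. How large could the effect be?** Let p be the study-eye DLEQ rate at a visit, f the share of LAL subjects with fellow-eye light in that visit's recall period, and e the erythropsia rate from that light. Suppose the eyes are independent and every fellow-eye episode is reported as study-eye erythropsia. Then

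observed rate = 1 − (1 − p)(1 − f·e), and added rate = (1 − p)·f·e.

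Section 6 gives 500 subjects at 2:1, so 500 × 2/3 ≈ 333 are in the LAL arm. The values of p, f and e are assumptions; the documents give none of them. With p = 5%:

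| f | e | Observed rate | Added points | Extra subjects of 333 |
|---|---|---|---|---|
| 10% | 5% | 1 − 0.95×0.995 = 5.5% | 0.5 | 1.6 |
| 25% | 10% | 1 − 0.95×0.975 = 7.4% | 2.4 | 7.9 |
| 50% | 20% | 1 − 0.95×0.90 = 14.5% | 9.5 | 31.6 |

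**The case against.** The strongest reply is that the key text cannot be seen. The DLEQ items are not supplied, and Section 6.7 has a gap where the assessment techniques are cited. The instrument may well ask about the study eye only. The CRFs are not supplied either, and because fellow-eye ocular adverse events are reported, some fellow-eye data must be collected. Section 7.2 also promises a detailed SAP before database lock, which could contain the split. All of this stands, and it is why the point is about what the plan should state and record, not about a demonstrated bias.

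The consequences are also limited. The rates are descriptive, and counting fellow-eye symptoms would overstate harm, which is the cautious direction in a safety study. Extra triggers lead to testing and do not themselves count as retinal damage. The mailed DLEQ reaches only subjects who have already reported erythropsia. This bears on priority. It does not make the rate attributable to the study eye, and estimating rates is what this study is for.

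Four stronger readings are tempting, and the documents do not support them.

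- *The DLEQ rate is inflated.* Without the items, inflation is possible but not shown.
- *Spontaneous reports inflate a study-eye rate.* They are triggers, not a listed rate. Where they become adverse events, the fellow eye is reported separately.
- *The effect is 1.4 to 11.2 points.* Setting e = p and taking 30-70% ever treated with p of 5-20% gives f·p·(1 − p) from 0.3×0.05×0.95 = 1.4 to 0.7×0.20×0.80 = 11.2 points. But the rate is reported at each visit, so f should be the share with fellow-eye light in that visit's recall period, which is smaller than the share ever treated.
- *The main rate should use only visits before fellow-eye light.* The fellow eye may have been treated long before enrolment, and subjects who choose a second LAL may differ from the rest. Dropping their visits could itself introduce selection.

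**Conclusion.** The point holds as a gap in attribution. The plan permits LDD light in the fellow eye during follow-up, reports a subject-completed outcome by study eye, and in its readable text gives the analyst no means of telling the two sources apart. The DLEQ and spontaneous-report triggers share the gap and could send study eyes for additional testing because of fellow-eye symptoms.

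The size is unknown. The illustrative range of about 0.5 to 9.5 points rests on assumed values of p, f and e, independent eyes and complete misattribution. Positive correlation between the eyes, or partial misattribution, would make it smaller. A reader might infer that the retinal-damage co-primary is miscounted. The documents do not support that: it counts LAL study eyes with damage, and the fellow eye would mainly affect who is tested. This is a cheap improvement to a descriptive safety analysis, not a flaw in the primary comparison.

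**What to change.** - On the CRF, record the fellow eye's IOL type and the date of every fellow-eye LDD treatment, including any before enrolment.
- State in Sections 5.2 and 7.6.3 that the DLEQ rate refers to the study eye.
- In Section 7.6.3, keep the all-visit DLEQ rate as the main summary. Add a sensitivity table that excludes visits whose recall period follows fellow-eye LDD treatment, with the recall period defined in the SAP.
- In the listings, flag every additional-testing trigger that follows fellow-eye LDD treatment.

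No trigger or treatment rule changes. The cost is a few CRF fields and one table. The restricted estimate will use fewer visits, possibly selected ones, so it belongs beside the main rate and not in its place.
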